5.2.8 Schedule of Vital Signs during and Post-Infusion

- 1. Immediately prior to infusion
- 2. During infusion: vital signs continually monitored & recorded every 5 minutes
- 3. Post Infusion: q 15 minutes x 4 (1st hour), q 30 minutes x 4 (next 2 hours), q 1 hour x 4 (next 4 hours), and then every 4 hours thereafter.

5.2.9 Post-Infusion Period

The day following infusion will be considered Post-Infusion Day 1, regardless of what time of the day the infusion was given. Post-infusion monitoring will include hemodynamics, infusion related toxicities (pulmonary, hepatic, and renal lab indices), and neurologic complications. Laboratory tests will include a CBC with differential, chemistry panel, hepatic function panel, and coagulation panel. As part of the pulmonary monitoring a chest x-ray will be performed and blood-oxygen saturation will be monitored by finger oximeter. In the event of pulmonary dysfunction, standard supportive therapy will be given. The research team will review the first 24 hours of post-infusion monitoring for AE/SAE's and determine if the subject is eligible for discharge home. Any serious adverse event as described in the Statistical Considerations section will be reported immediately and referred to the DSMB and evaluated for potential relationship to the protocol.

Prior to discharge, the parent(s)/LAR will be given detailed instructions regarding signs and symptoms of infection such as fever, malaise, and chills and told to check the subject's body temperature twice daily for three weeks after discharge (through post-infusion day 21). Parents(s)/LAR will be instructed to immediately report neurological changes or seizure activity to the research team. A CBC and basic chemistry panel will be obtained 21 days post-infusion (+/- 7 days). Parent(s)/LAR will be given the option of having the lab tests performed by their PCP or, for local families, here at UTHealth. The research team will have daily contact with the parent(s)/LAR through post-infusion day 21. Monitoring information will be recorded on the case report form and any reports of abnormalities will be relayed to the study PI/Co PI immediately. If indicated, the parent(s)/LAR will be instructed to have the subject seen be their PCP for further evaluation. Local families may opt to be seen by the research team for adverse events evaluation.

After discharge, the subject's PCP will be given discharge summary information. The PCP will be asked to consult with the study PI on any AE/SAE's post-infusion to ensure that appropriate therapy/treatment is given to the subject.

5.2.10 Cross-Over and Follow-Up Visits

As part of the trial, the subjects will return to The University of Texas Health Science Center at Houston for 3 follow-up visits: 6 months (+/- 14 days), 1 year post-treatment (+/- 21 days), and 2 years post-treatment (+/- 21 days). Each visit will take place over 1-2 days, and the subject will undergo outpatient assessments which include physical and videotaped neurological exams, laboratory tests, chest radiograph, oxygen

saturation monitoring, psychological testing, and quality of life measures. DTMRI will be performed at the 1 and 2 year post-treatment visits.

Prior to scheduling the 1 year follow-up visit, the treatment blind will be broken and the parent(s) notified. At this time, the parent(s) of children in the placebo group may choose to have their child admitted to the Children's Memorial Hermann Hospital Pediatric ICU/MICU for cord blood cell infusion. If the subject's parent(s) agrees to the cord blood infusion, the study coordinator will notify the Director of GSCL of the scheduled visit date. The Director will then request that the cord blood be shipped from CBR. The frozen cord blood unit will be shipped overnight to the GSCL 7 – 14 days prior to the scheduled procedure. The cord blood will be kept frozen until the morning of the infusion. All procedures will be followed in the same manner as was done for the Treatment Group.

5.3 Handling of Cord Blood/BMMNC Interventions

Transportation, processing, assessing and quality assurance at GSCL are described in the Chemistry & Manufacturing section of the IND

5.4 Pre-Infusion Medications (All Groups)

Thirty minutes prior to the infusion, all subjects (regardless of treatment assignment) will receive intravenous Benadryl 0.5mg/Kg and Solu-Medrol 0.5mg/Kg. Additionally, the following medications will be ordered prior to the infusion and kept at the subjects' bedside: Benadryl 50 mg for injection, Epinephrine 1:10,000 – 10 mL for injection and Hydrocortisone 100 mg for injection (or Solu-Medrol 0.5mg/Kg).

5.5 Prohibited Interventions

Subjects may not be enrolled in other interventional research protocols while participating in this study.

6. CLINICAL AND LABORARTORY EVALUATIONS

- 6.1 Schedule of Events (See Appendix A)
- 6.2 Infusion Toxicity Complications
- 6.2.1 Hemodynamic Instability

Subjects will be admitted to the pediatric at Children's Memorial Hermann Hospital following the baseline outpatient visit and will be monitored continuously until discharge as described in previous sections. A primary concern is the precipitation of hemodynamic instability associated with infusion-related toxicities of cellular product transplant. It has been reported that hypotension, hypertension and bradycardia can occur from transplantation of cellular product that has been cryopreserved in dimethylsulfoxide (DMSO) and RBC depletion. To minimize the effect of these, our hUCB product will be washed according to Standard Operating Procedures prior to

infusion. However, it is possible that some quantity of DMSO will remain. To minimize the risk of hemodynamic instability, maintenance + an additional 10 – 40mL/Kg intravenous 0.9% saline volume replacement will occur concomitantly with the cellular product infusion. Blood pressure elevation will be defined as an increment of more than 20% from the baseline value at the beginning of the infusion (Konuma, 2008). An adverse event will be defined as a sustained (> 10 minutes) >20% decrease in MAP. Transient decreases in the mean arterial pressure (MAP) that respond to fluid infusion or inotropes will not be considered adverse events. Prolongation of capillary refill greater than 2 seconds from baseline as well as a greater than 20% change in heart rate during the procedure will prompt an evaluation as to the etiology of the change in hemodynamic status. Bradycardia, defined by a sustained reduction in heart rate, less than 40beats/min, that is unresponsive to intravenous fluid or inotrope support will be considered an adverse event. Restoration of hemodynamics to baseline will allow resumption of infusion. Inability to transfuse will preclude further participation in the study, though the subject will be followed for data collection per protocol.

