6.2.2 Pulmonary Complications

A concern exists regarding the systemic infusion of leukocytes in a concentrated manner. Theoretically, activated monocytes could function to enhance polymorphonuclear leukocytes (PMN) migration into the lung, as the lung is the primary "first pass" filter for intravenous infusion of any cellular product. PMN mediated organ injury typically occurs over a 6 – 24 hour time frame. Based on this, chest radiographs will be performed and evaluated at Baseline and on Post-Infusion Day 1. Additionally, blood-oxygen saturation will be monitored by finger pulse oximetery (SpO₂). Moderate respiratory dysfunction within the first 24 hours post – infusion will be considered an adverse event but will not warrant stopping the trial unless recommended by the DSMB. In the event of pulmonary dysfunction, standard supportive therapy will be given. Pulmonary symptoms/events corresponding to the CTCAE v4.0 Grade 3 will trigger the stopping rules described in section 10.

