10.6.2 Definitions [21CFR310.305]

10.6.2.1 Adverse Experience

Any adverse event associated with the use of a drug or biologic in humans, whether or not considered drug related. For this protocol, temporally association with the use of the cellular product will be considered.

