10.6.2.4 Serious Adverse Experience

Any adverse experience that results in any of the following outcomes: Death, a life-threatening adverse experience, inpatient hospitalization or prolongation of existing hospitalization, a persistent or significant disability/incapacity, or a congenital anomaly/birth defect. Important medical events that may not result in death, be life-threatening, or require hospitalization may be considered a serious adverse drug experience when, based upon appropriate medical judgment, they may jeopardize the patient or subject and may require medical or surgical intervention to prevent one of the outcomes listed in this definition.

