10.7 Recording Adverse Experiences

Safety data will be recorded on CRFs designed for this purpose. Adverse experiences will be collected from the time of randomization until completion of study visits or until 30 days after premature withdraw from the study. If an abnormal value or result is determined by the investigator to be clinically significant and/or temporally related, the adverse experience will be recorded on the appropriate CRF.

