10.7.1 Grading Criteria

The severity of adverse events experienced by the subjects will be graded according to the criteria set forth in the National Cancer Institute's Common Toxicity Criteria for Adverse Events Version 4.0. This document (CTCAE v4.0) provides a common language to describe levels of severity, to analyze and interpret data, and to articulate the clinical significance of all adverse events.

Adverse events will be graded on a scale from 1 to 5 according to the following standards in the NCI-CTCAE:

Grade 1 = mild adverse event

Grade 2 = moderate adverse event

Grade 3 = severe and undesirable adverse event

Grade 4 = life-threatening or disabling adverse event

Grade 5 = death

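### Section 6.2.1 excludes transient MAP falls reversed with inotropes from the adverse events, section 10.7 would record them, and no text says which governs

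*Combined protocol and SAP*

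**What the plan says.** Section 6.2.1 (Hemodynamic Instability) calls hemodynamic instability a primary concern of the infusion. It sets the blood-pressure threshold: "An adverse event will be defined as a sustained (> 10 minutes) >20% decrease in MAP". It then adds: "Transient decreases in the mean arterial pressure (MAP) that respond to fluid infusion or inotropes will not be considered adverse events". The exclusion has no limit on the depth of the fall or on how much drug support was needed. For bradycardia (a sustained rate under 40 beats/min), 6.2.1 names only the kind "that is unresponsive to intravenous fluid or inotrope support will be considered an adverse event".

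Section 10 is written more broadly. Section 10.6.2.1 defines an adverse experience as "Any adverse event associated with the use of a drug or biologic in humans, whether or not considered drug related", and says that temporal association with the cell product will be considered. Section 10.7 reads: "If an abnormal value or result is determined by the investigator to be clinically significant and/or temporally related, the adverse experience will be recorded". Section 10.7.1 grades severity from the bottom of the scale ("Grade 1 = mild adverse event"). Section 10.6.2.4 allows an important medical event to be judged serious if it "may jeopardize the patient or subject and may require medical or surgical intervention to prevent one of the outcomes listed in this definition".

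Section 9.1.1 points to section 6.2 when it lists SAEs, AEs and death for the exploratory time-to-event work. Section 9.2 describes the trial as primarily a safety study.

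**The concern.** The two rules give different answers for the same event. Suppose a child's MAP falls during infusion, an inotrope is given, and the pressure recovers within ten minutes. Under 6.2.1 this is not an adverse event. Under 10.7 it is an abnormal value with an obvious temporal relation to the infusion, so it is recorded. Section 6.2.1 also lets the infusion resume once hemodynamics return to baseline. Read literally, an infusion could be interrupted, a vasoactive drug given and the infusion completed with no adverse event on file.

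What is at stake is the completeness of the safety tables. An event ruled out at the definition may never be graded under 10.7.1, assessed for seriousness under 10.6.2.4, or considered under stopping rule 5 in 10.8.1, which applies to graded adverse events. The standing DSMB report format (Appendix C) lists adverse events and whether the child is hypertensive, but has no hypotension item. Unless someone asks for more, the adverse-event line is the only named route by which hypotension reaches that report.

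**Working it through.** **Step 1. Which events are in dispute.** *Transient* is not defined in 6.2.1; I read it by contrast with the 10-minute threshold beside it.

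| Event during infusion | 6.2.1 | 10.7 |
|---|---|---|
| MAP fall >20% lasting >10 min, treated or not | Adverse event | Recorded |
| Transient fall, responds to fluid alone | Not an adverse event | Recorded if judged clinically significant and/or temporally related |
| Transient fall, responds to an inotrope | Not an adverse event | Same test; temporal relation plain |
| Sustained rate <40/min, responds to an inotrope | Not named, so outside by implication | Same test |

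The first row agrees. The others do not, and the two inotrope rows matter most because a drug was needed.

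**Step 2. Is there a precedence rule?** No section states one. The nearest text is the pointer in 9.1.1 to section 6.2. It is a cross-reference inside an exploratory analysis and does not settle what is recorded. If anything, it makes exclusion from the count more likely.

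**Step 3. Consistency with neighbouring text.** Section 6.2.2 says moderate respiratory dysfunction in the first 24 hours "will be considered an adverse event but will not warrant stopping the trial unless recommended by the DSMB". Section 6.2.5 records other neurologic changes within 12 hours of infusion as adverse events. Neither exempts an event because treatment worked.

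**Step 4. Scale.** The plan gives no figure to reproduce and no rate for inotrope-treated falls. The inputs are 30 children, 15 per product arm, randomized 2:1 (section 3). So 30 × 2/3 = 20 receive cells at baseline (10 per product) and 10 receive placebo. Up to 20 + 10 = 30 receive cells if every placebo child crosses over.

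Exact (Clopper-Pearson) 95% intervals, with one event omitted or recorded:

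| Denominator | Omitted | Recorded |
|---|---|---|
| One product, baseline (10) | 0/10: 0 to 30.9% | 1/10 = 10.0%: 0.3 to 44.5% |
| All cells, baseline (20) | 0/20: 0 to 16.8% | 1/20 = 5.0%: 0.1 to 24.9% |
| All cells, with full crossover (30) | 0/30: 0 to 11.6% | 1/30 = 3.3%: 0.1 to 17.2% |

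With zero events the upper limit is 1 − 0.025^(1/n); for n = 20, 1 − 0.025^(0.05) = 0.168.

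The chance that at least one such fall occurs is 1 − (1 − p)^n, where p is an assumed rate per cell infusion:

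| Assumed p | n = 20 | n = 30 |
|---|---|---|
| 1% | 18% | 26% |
| 5% | 64% | 79% |
| 10% | 88% | 96% |

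For example, 1 − 0.95^20 = 0.642. At the low end there may be none. The pooled rows treat both products as having one rate. That is a simplification, since 6.2.1 links reported hypotension to cryopreserved product.

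**The case against.** The strongest reply is that 6.2.1 is the specific operational definition and should prevail. Section 10.6.2.1 is circular, defining an adverse experience as an adverse event, and sets no blood-pressure threshold to contradict 6.2.1. Thresholds are normal in section 6.2: the pulmonary text also has one, at moderate dysfunction. Section 10.7.1 grades events once identified and does not make every deviation an event. All of that is fair, but it does not dispose of 10.7, which is a recording rule with its own test and no exception. The protocol does not say the specific section wins.

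Several stronger readings are tempting and should be resisted.

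- A reader might infer that all drug-treated hypotension is lost. It is not: a fall of more than 20% lasting over 10 minutes counts even if an inotrope was given.
- A reader might infer a direct contradiction with 10.6.2.4. That clause is discretionary and rests on medical judgment. A brief, reversed fall is not serious by default.
- A reader might take the bedside epinephrine in 5.4 as evidence that inotrope use is expected. It is listed with Benadryl and hydrocortisone, which reads as an allergy kit, and 10.8 handles anaphylaxis by stopping the infusion.
- A reader might argue that post-infusion readings 15 to 240 minutes apart cannot time a 10-minute fall. Section 6.2.1 requires continuous monitoring until discharge.
- A reader might infer a danger to the children or a biased primary outcome. Vital signs are recorded every 5 minutes during infusion, the team reviews the first 24 hours (5.1.7, 5.2.9), and the Medical Safety Monitor reviews safety data in real time (10.6.1). Hypotension is not among the primary measures in 1.1.

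The objection also rightly shows that removing inotropes from the exclusion is not enough by itself. Brief fluid-responsive falls would still meet the temporal test in 10.7, so a governing sentence is needed.

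**Conclusion.** The concern holds in a limited form and should be corrected. Section 6.2.1 excludes transient inotrope-treated MAP falls by a written rule, and inotrope-responsive bradycardia by implication. Section 10.7 would record them, and the protocol does not resolve the difference. The consequence is a possibly incomplete count of hypotension and bradycardia in a trial whose main purpose is safety. The underlying readings should be recoverable from the vital-sign record.

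The number of events affected is unknown. One omitted event moves the baseline cell-treated count from 1/20 to 0/20, as any single unrecorded event would; the difference here is that the plan's own rule removes it. The conclusion rests on reading *transient* as not sustained beyond 10 minutes and on the absence of any precedence statement. The 1%, 5% and 10% rates are illustrative assumptions and the conclusion does not depend on them.

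**What to change.** In 6.2.1:

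1. Delete *or inotropes* from the exclusion.
2. State that any MAP fall or bradycardia treated with an inotrope, whatever its length, is recorded as an adverse event, graded under 10.7.1, assessed for seriousness under 10.6.2.4, and listed by product (BMMNC, hUCB) and placebo.
3. Add one governing sentence: 6.2.1 governs brief falls that resolve with fluid alone, which are not recorded unless the investigator judges them clinically significant; 10.7 governs otherwise.

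Keeping brief fluid-responsive falls out is reasonable because 6.2.1 already gives extra saline alongside the cell infusion, so a response to fluid is hard to separate from routine management. Giving an inotrope is a distinct act that can be counted.

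The cost is a wording change, a place to record start, end and treatment (the case report forms are not in the documents, so some of this may already be captured), and one table line. The downside is a little extra charting and a slightly higher reported adverse-event count.

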6.2.2 Pulmonary Complications

A concern exists regarding the systemic infusion of leukocytes in a concentrated manner. Theoretically, activated monocytes could function to enhance polymorphonuclear leukocytes (PMN) migration into the lung, as the lung is the primary "first pass" filter for intravenous infusion of any cellular product. PMN mediated organ injury typically occurs over a 6 – 24 hour time frame. Based on this, chest radiographs will be performed and evaluated at Baseline and on Post-Infusion Day 1. Additionally, blood-oxygen saturation will be monitored by finger pulse oximetery (SpO₂). Moderate respiratory dysfunction within the first 24 hours post – infusion will be considered an adverse event but will not warrant stopping the trial unless recommended by the DSMB. In the event of pulmonary dysfunction, standard supportive therapy will be given. Pulmonary symptoms/events corresponding to the CTCAE v4.0 Grade 3 will trigger the stopping rules described in section 10.

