6.2.4 Renal Complications

DMSO induces hemolysis of contaminating red blood cells during the hUCB storage and may also induce in vivo hemolysis and ultimately pigment nephropathy (Smith, 1987). To minimize the effect of these, our hUCB product will be washed according to Standard Operating Procedures prior to infusion. Though unlikely, it is possible that some quantity of DMSO will remain which could cause toxicity. Renal function/events corresponding to the CTCAE v4.0 Grade 3 will trigger the stopping rules.

IRB NUMBER: HSC-MS-12-0876
UTHeath
The University of Texas
The University of Texas

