6.2.5 Neurologic Complications

The subject's acute neurologic status will be monitored hourly until discharged. Hourly GCS, pupillary size/reactivity, motor/sensory evaluation of extremities, and any seizure activity will be recorded from time of infusion to discharge. *Grade 3 – 5 central nervous* system event as defined in the NCI CTCAE v4.0 occurring within 12 hours of cellular product infusion will trigger the stopping rules. Other changes temporally related to cellular product infusion (those events occurring within 12 hours of infusion) will be considered associated with the protocol and recorded as an adverse event.

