10.8.1 Stopping Rules

- 1. ANY death that is deemed by the DSMB to be related or possibly related to the study treatment.
- 2. Both P:F ratio < 70 AND PaC02 > 90 within the first 48 hours post BM infusion occurring in a single subject.
- 3. AST/ALT > 900 U/dl in the first 24 hours post infusion occurring in a single subject.
- 4. Grade 4 5 CNS cerebrovascular ischemia event or Grade 4 5 seizure event as defined in the NCI CTCAE v4.0 occurring within 12 hours of BMMNCs or Cord blood Cell re-infusion.
- 5. Any Grade 4 5 Adverse Event as defined in the NCI CTCAE v4.0 and determined to be temporally-related by the Medical Safety Monitor and/or DSMB.

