10.9 Communication and Reporting Serious Adverse Events (SAEs)

Any grade 4-5 adverse event (CTCAE v4.0) deemed by the MSM and/or the DSMB to be temporally associated with the treatment will prompt cessation and trigger the stopping rules. Triggering the stopping rules will prompt notification of the FDA and IRB. If a patient that receives study treatment dies, and the DSMB determines that it may be related to the treatment, then the study will be terminated and a comprehensive safety review undertaken.

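### Section 6.2 says Grade 3 pulmonary, renal and CNS events trigger the stopping rules, but section 10 holds no Grade 3 rule and no text says which section governs

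*Combined protocol and SAP*

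**What the plan says.** Sections 6.2.2 to 6.2.5 set a trigger for each organ:

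- **Pulmonary (6.2.2).** "Pulmonary symptoms/events corresponding to the CTCAE v4.0 Grade 3 will trigger the stopping rules described in section 10". The sentence gives no time window and does not limit the product. Just before it, moderate dysfunction in the first 24 hours is called an adverse event that "will not warrant stopping the trial unless recommended by the DSMB".
- **Hepatic (6.2.3).** AST/ALT above 900 U/dL in the first 24 hours, described as a Grade 4 level.
- **Renal (6.2.4).** "Renal function/events corresponding to the CTCAE v4.0 Grade 3 will trigger the stopping rules". No window is given.
- **CNS (6.2.5).** The trigger is a Grade 3 to 5 central nervous "system event as defined in the NCI CTCAE v4.0 occurring within 12 hours of cellular product infusion will trigger the stopping rules".

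Section 10.8.1 lists five rules:

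1. A death that the DSMB judges related or possibly related to treatment.
2. P:F ratio below 70 together with PaCO2 above 90 within 48 hours, after bone marrow infusion only.
3. AST/ALT above 900 U/dL within 24 hours.
4. Grade 4 to 5 cerebrovascular ischemia or seizure, "as defined in the NCI CTCAE v4.0 occurring within 12 hours of BMMNCs or Cord blood Cell re-infusion".
5. Any Grade 4 to 5 "Adverse Event as defined in the NCI CTCAE v4.0 and determined to be temporally-related by the Medical Safety Monitor and/or DSMB".

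Section 10.9 repeats the general threshold: "Any grade 4-5 adverse event (CTCAE v4.0) deemed by the MSM and/or the DSMB to be temporally associated with the treatment" leads to cessation and sets off the rules. It then adds: "Triggering the stopping rules will prompt notification of the FDA and IRB".

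**The concern.** Safety of the infusions in children is the primary objective (section 1.1), and section 10.7.1 grades a severe event as Grade 3. A reader of section 6.2 would conclude that one severe respiratory, renal or early CNS event sets off the stopping rules. A reader of section 10, where section 6.2.2 sends them, finds no rule that such an event meets. Site staff, the Medical Safety Monitor (MSM), the DSMB and the IRB could each follow the protocol faithfully and act differently. At stake are whether the stopping rules are in force after such an event and whether the FDA and IRB must be told because of it.

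**Working it through.** The plan gives no operating characteristic for its stopping rules, so there is no figure to reproduce. The check sets the two sections side by side and then looks for a statement of precedence.

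| Organ | Section 6.2 | Organ rule in 10.8.1 | General rule (rule 5 and 10.9) | Match? |
|---|---|---|---|---|
| Pulmonary | Grade 3, no window, no product limit | Rule 2: gas exchange, no grade, 48 h, bone marrow only | Grade 4–5, temporal relation judged by MSM and/or DSMB | No |
| Hepatic | AST/ALT > 900, 24 h, called Grade 4 | Rule 3: AST/ALT > 900, 24 h | Grade 4–5 | Yes |
| Renal | Grade 3, no window | None | Grade 4–5, as above | No |
| CNS | Grade 3–5, any CNS event, 12 h | Rule 4: Grade 4–5, ischemia or seizure only, 12 h | Grade 4–5, as above | No |

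**Count.** Four organ triggers, one matched (hepatic), so 4 − 1 = 3 have no matching rule.

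**Pulmonary.** Section 6.2.2 says its rule is described in section 10. The only pulmonary rule there is rule 2, which carries no CTCAE grade. Whether it equals any particular grade cannot be settled from the documents, but it is not written as a Grade 3 rule.

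**Renal.** With no organ rule in section 10, the only comparison is with rule 5, which starts at Grade 4.

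**CNS.** The two texts share the 12-hour window but differ in grade (3 against 4) and in scope. A Grade 4 CNS event that is neither ischemia nor seizure is an automatic trigger under section 6.2.5. Under section 10.8.1 it reaches only rule 5, which needs a judgement of temporal relation.

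**Is Grade 3 a typing slip?** Probably not. It stands in three subsections, and section 6.2.2 separates moderate dysfunction, which does not by itself stop the trial, from Grade 3, which triggers the rules. That order fits section 10.7.1, where Grade 2 is moderate and Grade 3 severe, although the sentence on moderate dysfunction cites no grade itself.

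**Precedence.** Section 8.3 only points to the stopping rules. Sections 10.3 to 10.6, 10.8, 10.9 and 11.3 and the DSMB charter (Appendix C) do not say which section governs.

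**Consequence.** In section 10.9, cessation is attached to a temporally associated Grade 4–5 event. Only notification of the FDA and IRB is expressly attached to triggering the rules.

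**Units.** Section 4.2 states the SGPT exclusion in U/L, while section 6.2.3 and rule 3 use U/dL. Since 1 L = 10 dL, 900 U/dL × 10 = 9,000 U/L, and 9,000 / 900 = 10. Read literally, the limit is ten times the same number in the eligibility unit.

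**Frequency.** None is calculated. Section 7.1 gives a 0.1–0.4% serious complication rate for marrow harvest, and section 3 names 10 to 15% as an incidence the trial could detect. Neither is an expected rate of Grade 3 pulmonary, renal or CNS events after infusion.

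**The case against.** The strongest reply is that the two sections add together. Section 10.8.1 lists sufficient conditions and never calls the list exclusive. A site that honours both sections would act at Grade 3 and breach neither, and overlap proves nothing because rules 4 and 5 already overlap. This has force against calling the texts flatly contradictory: nothing in section 10 says that a Grade 3 event does not count. It does not remove the defect, because section 6.2.2 says the rule is set out in section 10 and it is not there. Someone working from the list in section 10.8.1 would miss three triggers.

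A second reply is that oversight limits the harm, and much of it stands. The MSM reviews safety data in real time (section 10.6.1). Serious adverse events are referred to the DSMB (sections 5.1.7 and 5.2.9), and the DSMB can recommend suspension or termination (Appendix C). But a Grade 3 event need not be serious, since section 10.6.2.4 defines seriousness by outcome. The charter also sends only unexpected and related serious events to the DSMB within 7 days; the others go with the standard reports. None of these safeguards sets the threshold.

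Four stronger readings are tempting and are not supported:

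- **That a Grade 3 trigger would oblige the trial to cease.** Section 10.9 ties cessation to Grade 4–5 events, so only notification follows expressly.
- **That three organs sit exactly one grade below section 10.** Only CNS has a graded organ rule to compare with; rule 2 has no grade and renal has no rule.
- **That the bone marrow limit in rule 2 is a slip of the pen.** No text shows that it was accidental, and rule 5 already covers temporally related Grade 4–5 events after cord blood. Widening it is a substantive change.
- **That severe events go unmonitored.** The safeguards above show otherwise.

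**Conclusion.** The point holds as an inconsistency in the safety thresholds that should be corrected. Three of the four organ triggers in section 6.2 (pulmonary, renal, CNS) have no matching rule in section 10, and nothing says which section governs. After a Grade 3 event it is therefore unclear whether the stopping rules, and at least the FDA and IRB notification, apply. The gap is mainly at Grade 3, because rule 5 reaches Grade 4–5 events of any organ and either product once judged temporally related. For CNS there is also the difference in scope between any event and ischemia or seizure. The AST/ALT unit is a separate threshold that is wrong as written; clinicians would probably read it as U/L.

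These conclusions rest on the wording alone and on no assumed event rate. One reading is assumed: the pulmonary and renal sentences name Grade 3 without adding higher grades, and are taken to mean Grade 3 or above.

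**What to change.** Make section 10.8.1 the single complete list and have section 6.2 refer to it. By default, carry over the more protective section 6.2 triggers:

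- **CNS:** any Grade 3–5 CNS event within 12 hours of infusion, replacing rule 4.
- **Pulmonary:** Grade 3 or higher after either product, with a stated post-infusion window. Delete rule 2 or keep it only as an explicit example, so that one pulmonary threshold remains.
- **Renal:** Grade 3 or higher, with a stated post-infusion window.
- **No added judgement:** do not make the pulmonary or renal trigger depend on an MSM or DSMB finding of temporal relation, which section 6.2 does not require.
- **Section 10.9:** amend it to the same thresholds, and say whether a trigger means cessation as well as notification.
- **AST/ALT:** write 900 U/L in section 6.2.3 and rule 3.

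If the sponsor and DSMB intend Grade 4–5 instead, change sections 6.2.2, 6.2.4 and 6.2.5 to that threshold and state whether the CNS rule covers all events or only ischemia and seizure.

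The cost is a protocol amendment, with no added patients, visits or procedures. Keeping Grade 3 makes a pause more likely than under a Grade 4 rule, by an amount the documents do not allow to be quantified. Choosing Grade 4–5 leaves Grade 3 events to MSM and DSMB judgement.
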